10. REGULATORY, ETHICAL AND LEGAL ISSUES

10.1 Declaration of Helsinki

The investigator will ensure that this study is conducted in full conformity with the seventh revision of the 1964 Declaration of Helsinki.

10.2 Good Clinical Practice

The study will be conducted in accordance with the guidelines laid down by the International Conference on Harmonisation for Good Clinical Practice (ICH GCP E6 guidelines).

10.3 Independent Ethics Committee Approval

10.3.1 Initial Approval

Prior to the enrolment of subjects, the REC must provide written approval of the conduct of the study at named sites, the protocol and any amendments, the Subject Information Sheet and Consent Form, any other written information that will be provided to the subjects, any advertisements that will be used and details of any subject compensation.

10.3.2 Approval of Amendments

Proposed amendments to the protocol and aforementioned documents must be submitted to the REC for approval as instructed by the Sponsor. Amendments requiring REC approval may be implemented only after a copy of the REC's approval letter has been obtained.

Amendments that are intended to eliminate an apparent immediate hazard to subjects may be implemented prior to receiving Sponsor or REC approval. However, in this case, approval must be obtained as soon as possible after implementation.

10.4 Annual Progress Reports

The REC will be sent annual progress reports in accordance with national requirements.

10.5 Annual Progress Reports and End of Trial Notification

The REC will be sent Annual Progress updates in order to facilitate their continuing review of the study (reference. ICH GCP E6 Section 3.1.4) and will be informed about the end of the trial, within the required timelines. The Annual Progress Report will detail all SAEs recorded.

PROSTAGRAM	Protocol no: 18HH4595	Sponsor: Imperial College London	V 1.01MAY2019
-------------------	---------------------------------	---	----------------------

10.6 HRA Approval

Health Research Authority (HRA) approval will be obtained prior to starting the study. Each participating site will confirm capacity and capability prior to commencing.

The HRA and all participating sites also need to be notified of all protocol amendments to assess whether the amendment affects the institutional approval for each site.

10.7 Other Required Approvals

None required as no ionising radiation or administration of radioactive substances are required in the protocol.

10.8 Non-Compliance and Serious Breaches

All protocol deviations and protocol violations will be reported via the eCRF/CRF and reviewed by the Chief Investigator and reported to the ICTU QA Manager on a monthly basis. Protocol violations will be reported to the Sponsor.

An assessment of whether the protocol deviation/violation constitutes a serious breach will be made.

A serious breach is defined as:

A breach of the conditions and principles of GCP in connection with a trial or the trial protocol, which is likely to affect to a significant degree:

- The safety or physical or mental integrity of the UK trial subjects; or
- The overall scientific value of the trial

The Sponsor will be notified within 24 hours of identifying a likely Serious Breach. If a decision is made that the incident constitutes a Serious Breach, this will be reported to the REC within 7 days of becoming aware of the serious breach.

10.9 Insurance and Indemnity and Sponsor

Imperial College London holds negligent harm and non-negligent harm insurance policies, which apply to this study. Imperial College London will act as the main Sponsor for this study. Delegated responsibilities will be assigned to the NHS trusts taking part in this study.

10.10 Trial Registration

The study will be registered on an International Standard Randomised Controlled Trial Number (ISRCTN) database in accordance with requirements of the International Committee of Medical Journal Editors (ICMJE) regulations.

PROSTAGRAM	Protocol no: 18HH4595	Sponsor: Imperial College London	V 1.01MAY2019
-------------------	---------------------------------	---	----------------------

10.11 Informed Consent

Subjects should be provided with a copy of the signed Subject Information Sheet/Informed Consent Form document. The original Informed Consent Form should be retained with the source documents.

10.12 Contact with General Practitioner

It is the investigator's responsibility to inform the subject's General Practitioner (where applicable) by letter that the subject is taking part in the study provided the subject agrees to this, and information to this effect is included in the Subject Information Sheet and Informed Consent. A copy of the letter should be filed in the medical notes.

10.13 Subject Confidentiality

The investigator must ensure that the subject's confidentiality is maintained. On the CRF or other documents submitted to the Sponsors, subjects will be identified by a subject ID number only. Documents that are not submitted to the Sponsor (e.g., signed informed consent form) should be kept in a strictly confidential file by the investigator.

The investigator shall permit direct access to subjects' records and source document for the purposes of monitoring, auditing, or inspection by the Sponsor, authorised representatives of the Sponsor, NHS and regulatory authorities.

10.14 Data Protection and Patient Confidentiality

The investigator will preserve the confidentiality of all participants taking part in the study, which will be conducted in accordance with the Data Protection Act.

10.15 End of Trial

The end of trial will be when all participants have completed their final follow-up visit (Visit 3) or at the request of the Trial Steering Committee. The final visit should take place within approximately one month of the biopsy procedure.

During this final visit, the study team will discuss the results of all screening study tests and biopsy results with the patient. Any side effects of the tests experienced by the patient can be discussed. This consultation marks the end of the study for participants.

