2.8 Performance objectives (MRI and US)

1. The proportion of men with screen-positive prostate ultrasound defined by a score of 3 or greater
2. The proportion of participants within each MRI score or US score of 1, 2, 3, 4 or 5
3. An evaluation of proportion of participants across each MRI and US score with no cancer, insignificant cancer and significant cancer with each test.
4. A comparison of the proportion of participants with a positive result for each screening test. A comparison of the proportion of men subsequently diagnosed with a clinically significant prostate cancer as defined by pre-specified histological definitions
5. Comparison of different testing combinations in terms of biopsy rates, detection of insignificant cancer and significant cancers
6. The correlation between imaging findings and DRE
7. The proportion of men who go onto definitive local or systemic treatment. In men who undergo radical prostatectomy the proportion who are upgraded at final histology

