2.14 Specification of efficacy parameters

OBJECTIVES		EFFICACY PARAMETER	TIME POINT & TOOL
Primary Objectives			
To determine the prevalence of screen-positive prostate MRI scans in the general male population aged 50 to 69 years		The proportion of men with a screening MRI score of 3 or greater	Visit 1 MRI reporting form
Secondary Objectives			
OTHER TEST PERFORMANCE OBJECTIVES (MRI AND US)	To determine the prevalence of positive test rate of US	The proportion of men with a screening US score of 3 or greater	Visit 1: US reporting form
	To establish the distribution of MRI and US scores in a screened population	The proportion of men across each MRI score	Visit 1: MRI & US reporting form
	To establish a threshold score that defines positivity of MRI and US in a screened population	Comparison of false positives & false negatives across each MRI & US scores	Visit 1 & 2: MRI, US and biopsy reporting form
	The overall agreement between PSA, US and MRI in the proportion of men with a screen positive result.	The proportion with a positive result for each screening test	Visit 1 PSA, US and MRI reporting form
	The overall agreement between PSA, US & MRI in proportion of men diagnosed with clinically significant prostate cancer on biopsy.	The proportion diagnosed with a clinically significant prostate cancer as defined histologically	Visit 1 & 2: PSA, MRI and biopsy reporting form
	To explore combinations & sequences of MRI, US and PSA	Comparison of biopsy rates, detection of insignificant/significant cancer	Visit 1 PSA, MRI, US reporting form
	To estimate overall imaging findings and DRE	Correlation between imaging & DRE	Visit 1 & 2 MRI, US & DRE form
	To report the clinical outcomes of men with any positive test result	The proportion who undergo treatment. If RRP the proportion upgraded at final histology	Visit 1-3: PSA, MRI and biopsy reporting form. Treatment outcomes

IP1 - PROSTAGRAM	Protocol No: 18HH4595	Sponsor: Imperial College London	V 1.2 01MAY2019
-------------------------	---------------------------------	--	------------------------

OBJECTIVES		ENDPOINT	TIME POINT & TOOL
FLUIDIC BIOMARKERS	To establish the positive test rate and distribution of biomarker panel scores	The proportion of men with a positive Episwitch biomarker panel and score	Visit 1: Biomarker panel reporting form

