### 10.3.6. Local or Systemic Treatment

Some patients may undergo definitive local or systemic treatment at follow-up. The procedures included are:

- Active surveillance
- Watchful waiting
- Focal treatment
- Radical prostatectomy
- Radical radiotherapy
- ADT.

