	Proportion of men who go onto definitive local or systemic treatment.	
 
MRI score: 
 
PIRADS score
 
Binary recorded overall MRI score
 
 
 
Ultrasound score: 
 
US score
 
Binary recorded overall US score
 
 
 
Dichotomised PSA level
 
Number of men who undergo definitive local or systemic treatment (Section 10.3.6)
 
	Visit 3 Treatment outcomes

Imperial Clinical Trials Unit	STATISTICAL ANALYSIS PLAN	PROSTAGRAM
-------------------------------	---------------------------	------------

Feasibility	Assess the acceptability of each diagnostic test with EBQ, PBQ and time taken to complete each screening test	
 
• Recorded responses to EBQ at visit 1, for all screening tests
 
• Recorded responses to PBQ at visit 1, for all screening tests
 
• Dichotomised test preference as measured by PBQ
 
• Patient factors: 
 
• Age: < 60 years vs ≥ 60 years
 
• Previous PSA: Yes vs No
 
• Previous DRE: Yes vs No
 
• Ethnicity: Black vs All other ethnicities
 
• Any first degree relative with history of prostate cancer: Yes vs No
 
• IMD quintiles
 
• Highest level of qualification: University degree vs All other responses
 
• Length of relevant procedure in minutes, excluding set up time, (Phlebotomy (PSA)/US/MRI)
 
• IPSS score: Mild vs Moderate/Severe
 
• CCI: Severe (≥ 2) vs Not severe (< 2)
 
• BMI: < 30kg/m^2 vs ≥ 30 kg/m^2
 
• EBQ component scores for each screening test.
 
 
 
• Time taken to complete each screening test procedure
 
• Time taken to complete each screening test procedure and set up
 
• Number of assessments by each screening test (MRI, ultrasound & PSA)
 
• Incidental findings reported for MRI & ultrasound screening tests
 
	Visit 1 Questionnaires at baseline PSA, ultrasound and MRI reporting forms
Other	Rates of biopsy related adverse events	Recorded biopsy related adverse events (Section 10.3.7)	Visit 3 Adverse events

Imperial Clinical Trials Unit	STATISTICAL ANALYSIS PLAN	PROSTAGRAM
-------------------------------	---------------------------	------------

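### The treatment end point is read at Visit 3, when biopsy results are discussed and participation ends, so Table 1.2.15 mixes management decisions with likely under-counted active treatment

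*Protocol*

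**What the plan says.** Protocol 2.8 (item 7) sets the end point as "The proportion of men who go onto definitive local or systemic treatment" and adds a second part: "In men who undergo radical prostatectomy the proportion who are upgraded at final histology". Protocol 2.14 gives its time point and tool as "Visit 1-3: PSA, MRI and biopsy reporting form. Treatment outcomes".

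The SAP keeps the first part (4.2.1, item 11). Its Table 2 (section 20.2.1) names the variable as "Number of men who undergo definitive local or systemic treatment (Section 10.3.6" and the source as "Visit 3 Treatment outcomes". SAP 10.3.6 says "Some patients may undergo definitive local or systemic treatment at follow-up" and lists six categories: two conservative policies (active surveillance and watchful waiting) and four active treatments (focal treatment, radical prostatectomy, radical radiotherapy and ADT). Table 1.2.15 gives each a column, as a proportion of screen-positive men for each test and cut-off.

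Protocol 5.5 and 10.15 place Visit 3 about a month after biopsy. On its content, 10.15 says "During this final visit, the study team will discuss the results of all screening study tests and biopsy results with the patient", and then "This consultation marks the end of the study for participants".

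**The concern.** The end point asks what happened to men after screening, but it is read at the visit where the result that would prompt treatment is discussed, and the study then closes for that man. A decision to watch exists as soon as it is made. Surgery, radiotherapy, focal treatment or ADT has to be arranged and begun before anyone can be said to have undergone it.

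Overtreatment is one of the harms that Protocol 1.1 gives as a reason for the study, and clinical outcomes of screen-positive men are a stated objective (Protocol 2.2, item 7). If Table 1.2.15 shows few radical treatments beside a larger surveillance column, a reader may conclude that screening by that test leads to little radical treatment. The figure may reflect only the reading date.

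**Working it through.** The plan states no treatment rate and no time from biopsy to treatment, so there is no figure to reproduce. The check sets the passages side by side.

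1. **When the end point is read.** Visit 3 in SAP Table 2; Visits 1 to 3 in Protocol 2.14. Neither goes later.
2. **When Visit 3 occurs.** About one month after biopsy (Protocol 5.5 and 10.15).
3. **What happens there.** Test and biopsy results are discussed, and participation ends (Protocol 10.15).
4. **What is collected there.** In the visit schedules (Protocol 5.4, SAP 5.5.2) the final visit carries questionnaires, adverse events with compliance, and resource use. There is no treatment row.
5. **What exists afterwards.** Both schedules have an optional long-term follow-up column. Protocol 5.5 makes linkage to national databases subject to optional consent and to future funding. SAP 4.2.5 marks linkage as outside the SAP.
6. **Whether a window is stated.** SAP 10.3.6 refers only to follow-up, and SAP 11.2.3 gives no time limit. SAP 12 notes that follow-up is short, but only as a reason to expect little loss to follow-up.
7. **What can be known by Visit 3.** For the two conservative policies, the decision itself, that day. For the four active treatments, only those begun within about a month of biopsy. One table thus holds two kinds of quantity.
8. **Upgrading.** This needs an operation and then its pathology report, so it comes later than the treatment count. Protocol 2.14 nevertheless ties it to Visits 1 to 3. SAP 4.2.1 does not list it. Staged SAP versions do not explain the gap: 4.2.1 does list items left to later papers, such as the correlation with rectal examination, and none of the secondary papers named at the front of the SAP mentions upgrading.

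**Illustration only.** Suppose time from biopsy to active treatment were exponential with median m months, and the reading were W months after biopsy. The share captured is 1 − 2^(−W/m).

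| W (months) | m = 1 | m = 2 | m = 3 | m = 6 |
|---|---|---|---|---|
| 0.5 | 29% | 16% | 11% | 6% |
| 1 | 50% | 29% | 21% | 11% |
| 1.5 | 65% | 41% | 29% | 16% |

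For example, W = 1 and m = 3 gives 1 − 2^(−1/3) = 1 − 0.794 = 0.206. The medians and the exponential shape are assumptions. The spread from 6% to 65% comes entirely from them and from W, so it shows only that the result depends on a quantity the documents do not supply.

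**The case against.** A reader might infer something stronger: that no treatment can be counted, so Table 1.2.15 will show proportions near zero. The documents do not support that, for two reasons.

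- Two of the six categories in SAP 10.3.6 are surveillance policies, which can be recorded at the Visit 3 consultation. Those columns need not be near zero.
- Protocol 10.15 says results are discussed at the final visit, not that they are first disclosed there. Protocol 5.3.2 unblinds men to their screening tests after biopsy without naming a visit, and Protocol 6.5 times the last questionnaires after the biopsy result. Some men may hear earlier, and some active treatment could begin before Visit 3. What is established is a short window, not impossibility.

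Later follow-up is also not wholly absent, because optional linkage exists. This helps little: it depends on funding not yet obtained and on consent, and it is outside the SAP. Men enrolled early may be treated before the trial as a whole closes, but nothing provides for collecting this after their own Visit 3.

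Finally, this is one of eleven test-performance end points in SAP 4.2.1. It is reported as proportions with no hypothesis test, and does not touch the primary analysis. That is right, and it limits the importance of the point. It does not make the columns comparable.

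**Conclusion.** The concern holds in this form. With treatment read at Visit 3 and no later in-study capture, Table 1.2.15 can record surveillance and watchful-waiting decisions but is likely to under-count the four active treatments. Presenting all six as treatment undergone misdescribes what is measured. Upgrading at prostatectomy would be largely unobservable on this timetable, and its absence from the SAP is unexplained.

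The direction rests on one assumption: that active treatment often starts more than about a month after biopsy. The documents neither confirm nor exclude this. The size cannot be estimated from them, and the illustration should not be quoted as a bias. The point should be corrected before the table is produced. It affects a secondary descriptive end point; the sample size and primary end point stand.

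**What to change.** Redefine the in-study end point as *management decision recorded at Visit 3*. Carry that wording through SAP 4.2.1, 10.3.6, 11.1.3 and 11.2.3, Table 1, Table 1.2.15 and Table 2, and check that the Visit 3 form records the decision. State that treatment actually received and upgrading at prostatectomy are not estimated from Visit 3 data. Either withdraw upgrading explicitly from this analysis or defer it to later follow-up, and reconcile Protocol 2.8 and 2.14 with that choice.

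The cost is mainly wording. The downside is that the in-study figure becomes intended management, and some men will later be managed differently.

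If the team also wants treatment received, it could extract hospital records at one fixed date and show each man's follow-up time. This is optional and not needed for the correction. It would collect data after the point that Protocol 10.15 calls the end of the study for participants, so it may need a consent check and a protocol amendment with ethics approval (Protocol 10.3.2). Linkage should not be named as the source for upgrading unless it is confirmed that the databases hold prostatectomy grade; the documents do not say that they do.

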10.16 Study Documentation and Data Storage

The study investigators and study site staff will comply with the requirements of the Data Protection Act 2018 concerning the collection, storage, processing and disclosure of personal information and will uphold the Act's core principles.

PROSTAGRAM	Protocol no: 18HH4595	Sponsor: Imperial College London	V 1.01MAY2019
-------------------	---------------------------------	---	----------------------

All research documentation and information will undergo a process of pseudonymisation where possible. Whilst within the study, patients will be identified by a unique study number, and the data in the CRF will be linked to this number. Research data will be entered onto a dedicated, secure, encrypted trial database, specifically constructed for the purpose. The study team will maintain the confidentiality of all patient data and will not disclose information by which patients may be identified to any third party other than those directly involved in the treatment of the patient and organisations for which the patient has given explicit consent for data transfer. Data within the NHS system such as patient notes, MRI reports and histopathology reports will remain confidential in accordance with NHS confidentiality code of practice.

Paper enrolment logs, including patients' names, NHS numbers and dates of birth, will be kept in the Investigator Site File, stored in a secure, code-locked store room within the designated Imperial College London facilities. Electronic enrolment logs will be kept on the Trust Computers stored in a locked office space within Imperial College London and Imperial College Healthcare NHS Trust premises. Access to these documents will be highly restricted and only be available to the relevant study team members.

Contact details

Contact details collected using online survey providers, will be encrypted during transit and at rest. All data collected from online surveys will be stored in the UK. Online survey used must remain fully compliant with GDPR legislation and European Privacy Laws. The list of online-responders will be exported to excel file and stored on Trust Computers. The GDPR transparency wording will be utilised to ensure online responders about their data being secured for a 2-year period and destroyed thereafter.

MRI and US files

All MRI will be stored in a secure and password-protected databank (XNAT: <https://www.xnat.org/about/>) held in Imperial College London Clinical Imaging Facility under university research governance protocols and standard operating procedures. All the US scans will be kept on the Ultrasound Machine used and backed-up onto an external hard-drive on regular basis. The US machine and the external hard-drive will be kept at a code-locked, secure room within Imperial College Clinical Imaging Facility.

The anonymised MRI images will be transferred to a university computer/laptop to allow the AI/CAD reporting. This computer/laptop is encrypted and password protected using high levels of security in accordance with the University protocols. On completion of the study, this data will be transferred to the University servers and the laptop hard-drive wiped.

PROSTAGRAM	Protocol no: 18HH4595	Sponsor: Imperial College London	V 1.01MAY2019
-------------------	---------------------------------	---	----------------------

11. DATA MANAGEMENT

11.1 Source Data

Source documentation is defined as the first time data appear, and may include original document, data and records (hospital records, clinical reports, MRI and Ultrasound reports, other procedure reports, laboratory notes, other data recorded at the pathology and biochemistry laboratories, etc.). Information in source documents (e.g. medical history) dated prior to the Informed Consent Form signature date may be used to verify patient suitability for the study.

Clinical records must be marked to indicate a subject has been enrolled into the clinical study.

The Investigator must ensure the availability of source documents from which the information on the eCRF was obtained. Where printouts and electronic medical records are provided as source documents, they should be signed and dated by a member of the adequately trained research team, to indicate that the data provided is a true reproduction of the original source document.

All study data may be inspected by sponsor and regulatory authorities by people working on behalf of the Sponsor, and by representatives of Regulatory Authorities, where it is relevant to this research.

